Evaluating the Impact of Surgical Theater's Patient Engagement 360VR Platform on Spinal Surgery
Patient Expectations and Experiences

NCT05334212

08/2019

Objectives

To evaluate usefulness of Surgical Theater's Patient Engagement 360VR platform in helping align patient expectations and improve patient satisfaction and understanding in spinal surgery consults.

Background

Surgical Theater is a company that has developed a platform which can be used to describe and explain spinal surgery to patient before they undergo the procedure. The platform specifically implements data from the patient's own MRI and CT scans, creating a 3d reconstruction that can be seen through a virtual reality lens. This technology was developed to help clarify any concerns patient's may have before surgery, and help them better appreciate what will occur in the OR. Surgical theater has FDA clearance for patient interaction and engagement. Our study is to take surgical theater into our clinics and, after a patient is defined as a surgical candidate, use surgical theater to provide spatial learning and comprehension through modeling so they better understand their surgical plan. Only the SRP system will be used for this study (Surgical Planner). The intervention is showing surgical theater to patients identified for surgery in clinic routinely. Surgical theater will be offered to all patients offered surgery. No other changes in practice will be done.

Inclusion and Exclusion Criteria for Experimental Group

Inclusion

1. Age range: 18-89
2. Patients undergoing elective lumbar or cervical spine surgeries
3. Those who are receiving Surgical Theater consultation as part of their clinical care

Exclusion

1. Age <18 years
2. Nonelective surgery due to emergency, trauma
3. Patients undergoing correction for spinal deformities

Inclusion and Exclusion Criteria for Control Group

Inclusion

1. Age range: 18-89
2. Patients undergoing elective lumbar or cervical spine surgeries
3. Patients who do not have a previous CT scan and thus are unable to undergo Surgical Theater Consultation

Exclusion

1. Age <18 years
2. Nonelective surgery due to emergency, trauma
3. Patients undergoing correction for spinal deformities

Number of Research Participants

We will enroll 90 subjects at UHCMC. 30 subjects will receive surgical theater consultation. 60 patients will not receive surgical theater consultation, and will their survey responses will thus serve as a "control".

Recruitment Methods

Patients will be consented and offered surgery as normally performed in clinical practice in the office setting. The patient will then be offered a simulation of their surgery on Surgical Theater's Virtual Reality Rehearsal Platform. Subjects will be approached in person at the end of their appointment with PI. Treating physician will be on the study team.

Setting

- 1) Southwest General Health Center – Patients will be given survey and offered 360VR consult
- 2) Southwest General Health Center – Patients at this institution will be approached
- 3) Southwest General Health Center – 360VR platform is at this institution

All study procedures will take place at Southwest General

Consent Process

The consent process will take place at the end of patient's consult with PI. The consent process will take place in a private location. Steps will be taken to review the concept of three dimensional modeling and spatial learning. We will emphasize that modeling and simulation do not account for complications or adverse events during surgery. We will clarify that modeling and simulation display the optimal technique and approach to their disease. We will also discuss with the patient the rationale of showing them a different approach to learning more about their surgery. The patient will then be offered a simulation of their surgery on Surgical Theater's Virtual Reality Rehearsal Platform and sign consent if they agree to use surgical theater platform

Sharing of Results with Research Participants

- Results will not be shared with research participants
- Results will not be shared with research participants' doctors

Study Design

This study is a non-randomized, survey

Study Procedures

We will review their imaging in person and discuss the virtual reality software. There is no risk in showing the 3-D reconstruction of their surgery. Surgical Theater 360VR Platform will be used, it has been approved for patient education purposes. No medical, educational records will be used to collect data. The surgical theater platform will be explained as a virtual reality device that will display the patient's radiological imaging in 3d.

Survey assessing patient's understanding, anxiety, and satisfaction (Surgical Theater Survey, attached to Smart Form) will be given immediately before and after 360VR session is completed. Surgical theater appointment and review will take 24 minutes. QOL surveys (EQ-5D-5L, NDI, Oswestry, RAPT, VR-12) will also be given before 360-VR, 6 week post-op, 3 month post op, and 6 month post op. All survey's will be administered by giving the patient a physical paper form that they will fill out. Time commitment for each survey is 2 minutes.

A control group will be chosen, which will consist of patients who are scheduled to undergo elective spinal surgery but will not receive a 360VR appointment. This control group will consist of patients who do not have a CT scan prior to surgery.

Survey assessing control group patients' understanding, anxiety, and satisfaction (Control Group Survey, attached to Smart Form) will be given immediately after presurgical consult with [name] and will take 5 minutes. QOL surveys (EQ-5D-5L, NDI, Oswestry, RAPT, VR-12) will also be given 6 week post-op, 3 month post op, and 6 month post op. All surveys will be administered by giving the patient a physical paper form that they will fill out. Time commitment for each survey is 2 minutes.

Study Timeline

	Screening	Visit 1	Visit 2	Visit 3	Visit 4
Estimated time requirement of visit	0	54 minutes	10 minutes	10 minutes	10 minutes
360VR Consult	0	24	0	0	0
QOL Survey	0	10	10	10	10
Surgical Theater Survey	0	10	0	0	0
Consent Procedures	0	10	0	0	0

Data to be Collected for your study (AFTER consent and HIPAA Authorization have been obtained)

- Outcome measures

- Patient-reported health status outcomes
 - EQ-5D Health-Related Quality of Life
 - Reports on 5 dimensions of health: Mobility, Self-care, Usual activities, Pain/Discomfort, Anxiety/Depression
 - ♣ Each score from 1-3
 - 0.0(death) to 1.0 (perfect health),
 - Pain Disability Questionnaire (PDQ)
 - 0-10 scale to assess how pain affects the ability to function across 15 categories.
 - 0 (optimal function) to 150 (total disability)
 - Patient satisfaction and understanding with HCHAPS
 - Understanding – before and after consult
 - Anxiety level – before and after consult
 - Satisfaction with consult
 - HCAHPS – Overall rating of hospital

- o Satisfied = 9 or 10 rating
- ♣ Surgical conversion rate
- ♣ Consult time including time spent with VR
 - Time points
 1. Before 360VR consult (Visit 1)
 2. Immediately after 360VR consult (Visit 1)
 3. Post-op 6 weeks (Visit 2)
 4. Post op 3 months (Visit 3)
 5. Post op 6 month (Visit 4)

Data Analysis Plan

Descriptive statistics summarizing patient population and surgical characteristics will be compared using chi-square for categorical variables and Students t-tests for continuous variables.

Associations of patient-reported satisfaction and understanding with changes in each patient-reported health measure will be estimated using linear regression analysis as well as multivariable linear regression models, adjusting for potential confounders.

Risks to Research Participants

Possible motion sickness with 360VR goggles. May feel uncomfortable with some QOL questions regarding depression and anxiety. To mitigate this, patients will be told to skip any questions they feel uncomfortable with and the presence of such questions will be outlined during consent process. There is a risk of breach of confidentiality which means that someone who is not listed in this form might view your data either by accident or from malicious actions they take to hack the data. We are protecting against this by using a Password-protected locked drawer in a locked office at Southwest General Hospital to store data.

Provisions to Protect the Privacy Interests of Research Participants

All study procedures will be done in a private room where no other patients will be present. Data will be protected via RedCap

Password-protected locked drawer in a locked office at Southwest General Hospital to store data. Drawer will be [name] on [name]. Only [name] will have access to the drawer. Data will be monitored weekly by [name]

Potential Benefit to Research Participants

This study aims to provide helpful information on the impact of implementing VR into spinal surgery consults. By providing quantitative evidence on how personalized VR can improve patient's experiences, this study could lay the ground-work needed for drastic developments in patient education. Additionally, the patients themselves may benefit by receiving a different perspective regarding their condition and its treatment.

Withdrawal of Research Participants

Subjects may withdraw at any time, or refuse to answer any survey questions.

Some surveys ask questions about depression and anxiety. For mitigation, a medical professional will be available to speak with patient if they feel uncomfortable at any point during the study. In the instance patient experiences suicidal ideation, the study team will assess the acuity of the complaint and address that complaint in 2 possible ways:

- 1) Referral to the closest emergency room if we feel from the history that there is a high probability of self-harm, or
- 2) Referral to a psychiatrist if the threat is not immediate.

Alternatives to Participation

The alternative to participation is to have the surgery described in the usual manner without the use of the VR device

Costs to Research Participants

N/A

Research Participant Compensation

N/A

Provisions to Monitor the Data to Ensure the Safety of Research Participants

Data accuracy and completion will be reviewed and monitored by the study's data coordinator and PI on a weekly basis. There will be no Data and Safety Monitoring Board or Committee for this study.

References

1. <https://www.sciencedirect.com/science/article/abs/pii/S0967586819307957>
2. https://academic.oup.com/neurosurgery/article-abstract/73/suppl_1/S122/2417519
3. https://journals.lww.com/retinajournal/Abstract/2018/09001/THE_INTEGRATIVE_SURGICAL_THEATER__Combining.13.aspx

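### If the control paragraph is followed, controls have no pre-operative QOL score, and change from before surgery is computable in at most 30 of 90 subjects

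*Combined protocol and SAP*

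**What the plan says.** Study Procedures describes the QOL schedule in two parallel paragraphs. In the 360VR group the five instruments "will also be given before 360-VR, 6 week post-op, 3 month post op, and 6 month post op". In the control group the sentence reads "QOL surveys (EQ-5D-5L, NDI, Oswestry, RAPT, VR-12) will also be given 6 week post-op, 3 month post op, and 6 month post op". The only form that paragraph gives controls before surgery is their own survey of understanding, anxiety and satisfaction: "Control Group Survey, attached to Smart Form) will be given immediately after presurgical consult with" the treating physician. It is not one of the five QOL instruments.

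Three other places bear on the schedule:

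- The Study Timeline shows a 10-minute QOL survey at Visit 1 and does not say which group it describes.
- The time-point list has two pre-operative entries. The first is "Before 360VR consult (Visit 1"), and the second falls just after the same VR consult. Controls have no such consult.
- Study Procedures also states: "No medical, educational records will be used to collect data".

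The Data Analysis Plan relates satisfaction and understanding "with changes in each patient-reported health measure", by linear and multivariable linear regression, "adjusting for potential confounders". It does not limit this to one group and does not define change. The health-status outcomes named in the data list are EQ-5D and PDQ. NDI, Oswestry, RAPT and VR-12 appear only in the survey schedule.

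**The concern.** A change score needs a starting value. Two thirds of the subjects get three post-operative QOL rounds but, by their own paragraph, no round before surgery. The regression on changes is the only model the plan states. If change means change from before surgery, controls drop out of it.

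If change means change between post-operative visits, controls can contribute, but their health before surgery stays unseen. Group membership is not random: controls are the patients without a CT scan. Pre-operative QOL is therefore an obvious candidate for the confounder adjustment that the plan promises, and it would be available in one group only.

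The gap has a deadline. A pre-operative score cannot be collected once the patient has had surgery, and the plan names no record source that could supply it.

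**Working it through.** **Inputs.** Group sizes of 30 and 60, total 90 (Number of Research Participants). Five QOL forms at 2 minutes each, and a 5-minute Control Group Survey (Study Procedures). Visit 1 entries of 24, 10, 10 and 10 minutes, total 54 (Study Timeline). The plan gives no alpha, power, effect size or dropout rate, so there is no sample-size calculation to reproduce.

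**Step 1: the plan's own figures.** 30 + 60 = 90, as stated. The QOL set takes 5 × 2 = 10 minutes, matching the timeline row. Visit 1 is 24 (VR consult) + 10 (QOL) + 10 (Surgical Theater Survey) + 10 (consent) = 54 minutes, as stated.

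**Step 2: whose visit the timeline describes.** The total of 54 needs the 24-minute VR consult and the Surgical Theater Survey, and controls have neither. A control visit with QOL forms would be 5 (Control Group Survey) + 10 (QOL) + 10 (consent, if the timeline figure applies) = 25 minutes. No column shows that, and the Control Group Survey has no row. The table fits a 360VR visit. This is an inference, because the table has no group label.

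**Step 3: the count if the control paragraph is followed.**

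| | 360VR | Control | Total |
|---|---|---|---|
| Subjects | 30 | 60 | 90 |
| QOL rounds per subject | 4 | 3 | |
| Rounds scheduled | 30 × 4 = 120 | 60 × 3 = 180 | 300 of 90 × 4 = 360 |
| Pre-to-post change computable, at most | 30 | 0 | 30 of 90 = 33% |

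The 360 − 300 = 60 missing rounds are all pre-operative, one for each control. Skipped forms or withdrawals lower the 30: an assumed loss of 10% to 30% leaves 27 to 21. If the timeline entry was meant for controls as well, the maximum is 90, and the table then contradicts the control paragraph.

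**Step 4: what each reading of the regression loses.**

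- Change from before surgery, all subjects: at most 30 usable instead of at most 90.
- Change between post-operative visits (say 6 weeks to 6 months), all subjects: up to 90 usable, with no pre-operative adjustment for controls.
- 360VR subjects only: no loss.

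**Step 5: illustration of precision.** Assume two-sided alpha 0.05, 80% power and a simple correlation. The smallest detectable correlation is r = tanh((1.960 + 0.842)/√(n − 3)).

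| | All answer | 20% loss (assumed) |
|---|---|---|
| 360VR only | n = 30: 0.49 | n = 24: 0.55 |
| Controls only | n = 60: 0.36 | n = 48: 0.40 |
| Pooled | n = 90: 0.29 | n = 72: 0.33 |

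Pooling requires that the two groups' differently named surveys can be combined. If they can, the loss is from 0.29 to 0.49 with full response. If they cannot, the 360VR estimate is unchanged and what is lost is the separate control estimate.

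**The case against.** The strongest reply is that the timeline does schedule a QOL survey at Visit 1 and names no group, so the control sentence may simply have dropped a time point in drafting. That is possible, and it is why the count of 30 is conditional. It does not remove the problem: a site following the control paragraph would hand out no QOL forms before surgery, and the two places have to be reconciled either way.

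Second, the impact is limited. The stated objective concerns expectations, satisfaction and understanding in consults. The regression population is not stated, and under two of the three readings in the working no subject is lost. This stands, and it caps the seriousness of the point. The loss of baseline adjustment for controls remains wherever controls are in the model.

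Third, the sentence excluding records sits in a paragraph about imaging review and the VR software, while the plan also intends to summarise surgical characteristics without naming their source. The sentence therefore does not prove that a pre-operative score could never be recovered. It does mean that the plan provides no route to one.

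A reader might go further and infer that the regression loses five outcomes. The text does not support that: only EQ-5D (scheduled as EQ-5D-5L) is both administered and named as a health-status outcome. The other four come in only if the regression's reference to each measure is read broadly. A reader might also infer that PDQ is collected from nobody, because it is in neither group's survey set. PDQ is listed under data to be collected, in a section whose time points include Visit 1 and the post-operative visits. Whether it is administered is undetermined and is a separate question.

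**Conclusion.** The point holds, conditionally, and should be fixed. As the control paragraph stands, 60 of 90 subjects (67%) have no scheduled pre-operative QOL score. Change from before surgery is then computable in at most 30, and pre-operative QOL cannot be used to adjust for differences in the controls. This assumes that the paragraph prevails over the unlabelled timeline entry, which the 54-minute total supports but does not prove. The link to the regression is firm for EQ-5D and depends on interpretation for NDI, Oswestry, RAPT and VR-12.

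It would be tempting to say that the trial's main comparison is compromised. The documents do not support that, because they specify no 360VR-versus-control comparison of QOL. The detectable correlations are illustrations under assumed alpha and power and do not measure harm to a stated target.

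**What to change.** 1. Schedule the same five QOL forms for controls at the presurgical visit, after consent and before surgery. The Control Group Survey should be completed first so that it stays immediately after the consult. Timing would then be comparable with the 360VR group: under Consent Process, "The consent process will take place at the end of" the consult, so that group's forms also follow consent and precede surgery. That section describes signing only for use of the platform, so the amendment should also state how controls consent.
2. Reconcile the control paragraph, the Study Timeline and the time-point list by labelling each by group. Add a Control Group Survey row and a pre-operative entry for controls.
3. In the Data Analysis Plan, define change as change from the pre-operative score, adjust for that score, and report controls without it as excluded from that analysis. Name the instruments that the regression covers.
4. Clarify separately whether PDQ is administered. The steps above do not settle that.

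**Cost.** Five forms × 2 minutes = 10 minutes per control, and 60 × 10 = 600 minutes, or 10 patient-hours. There are 60 × 5 = 300 extra paper forms to handle and to include in the weekly accuracy and completeness review. If control consent takes 10 minutes (assumed), a control's study time at that visit rises from 5 + 10 = 15 to 25 minutes. A protocol amendment is needed, but no new visit.

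### The Data Analysis Plan states no 360VR-versus-control and no before-versus-after analysis of the understanding, satisfaction and anxiety surveys, and its only model estimates something else

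*Combined protocol and SAP*

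**What the plan says.** The Objectives section sets out to evaluate the usefulness of the platform "in helping align patient expectations and improve patient satisfaction and understanding in spinal surgery consults". Under Number of Research Participants, 30 patients receive the consultation, and "60 patients will not receive surgical theater consultation, and will their survey responses will thus serve as a" control.

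Under Study Procedures, the 360VR group's survey of understanding, anxiety and satisfaction "will be given immediately before and after 360VR session is completed". Controls complete one survey on the same three topics, straight after the presurgical consult. The data list marks understanding and anxiety as measured both before and after, but gives satisfaction with the consult no such label. It also lists an HCAHPS hospital rating, with 9 or 10 counted as satisfied.

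The Data Analysis Plan has two sentences. The first applies chi-square and t-tests to characteristics of the patients and their operations, without naming the groups compared. The second reads "Associations of patient-reported satisfaction and understanding with changes in each patient-reported health measure will be estimated using linear regression analysis", and adds multivariable versions adjusted for confounders that it does not list. No other section contains an analysis.

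**The concern.** The objective, the control group and the timing of the surveys all point to two contrasts: 360VR against control after the consult, and before against after within the 360VR group. The plan states neither. Its one model takes satisfaction and understanding, the outcomes that 360VR is meant to change, and relates them to changes in health measures.

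A study run to this plan could report every planned result and still say nothing about whether 360VR improved satisfaction or understanding. The section on potential benefit nevertheless promises numerical evidence on what VR does for patients' experience. If the missing contrasts are added once the data are in hand, the outcome, contrast and adjustment set can be chosen with the results in view.

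**Working it through.** **1. Measurement against analysis.** The plan states no figure on this point, so there is none to reproduce. Each survey outcome is set against the two planned analyses:

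- *Understanding*: measured before and after 360VR, and after the consult in controls. Planned use: related to health change only.
- *Satisfaction*: measured at least after the consult in both groups. Planned use: related to health change only.
- *Survey anxiety*: measured before and after 360VR, and after the consult in controls. Planned use: none.

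Of the two contrasts for each outcome, none is planned.

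**2. What the stated model estimates.** Write it as health change = a + b × satisfaction + c × covariates + error. The reported quantity is b. If study group were one of the covariates, its coefficient would be the group difference in health change at equal satisfaction. If the model is turned round, with satisfaction as the outcome, the group coefficient is a difference in satisfaction at equal later health change, so it conditions on something measured after the operation. Neither is the effect of 360VR on satisfaction.

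A simulation with the study's group sizes (30 and 60; 4,000 replicates; satisfaction = effect × group + noise; health change = b × satisfaction + noise; unit-variance noise) gave:

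| True 360VR effect (SD) | True b | Mean fitted slope | Mean group difference |
|---|---|---|---|
| 0 | 0 | 0.002 | 0.002 |
| 0 | 0.5 | 0.500 | 0.006 |
| 0.5 | 0 | -0.001 | 0.496 |
| 0.5 | 0.5 | 0.498 | 0.499 |
| 1.0 | 0 | 0.001 | 1.004 |
| 1.0 | 0.5 | 0.501 | 1.003 |

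The slope follows b whatever 360VR does. Only the group difference follows the 360VR effect.

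**3. Precision of the analyses to be added.** Group sizes come from the protocol. Alpha, power, score type and completeness are not given there. Assumed: two-sided alpha 0.05, 80% power, roughly continuous scores, no missing data.

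- Group contrast, 30 versus 60: the standard error in SD units is √(1/30 + 1/60) = √0.05 = 0.2236. The 95% half-width is t(88) × 0.2236 = 1.987 × 0.2236 = 0.444. The detectable difference is 0.633 SD by noncentral t (normal approximation: 2.802 × 0.2236 = 0.626).
- The same contrast if covariates explain an assumed share R² of group membership: 0.633/√(1 − R²). At R² = 0.10 this is 0.633/0.949 = 0.67; at 0.20 it is 0.633/0.894 = 0.71. Any gain from outcome variance explained comes after that.
- Paired change, n = 30: half-width t(29)/√30 = 2.045/5.477 = 0.373 SD of the change. Detectable change is 0.529 SD by noncentral t (normal approximation 0.511).

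**4. Why a primary is needed.** Three outcomes × two contrasts = 6 tests, or 5 if satisfaction is asked only once. If the tests were independent, the chance of at least one false positive at 0.05 is 1 − 0.95⁵ = 0.226 to 1 − 0.95⁶ = 0.265. Correlation would lower it.

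**The case against.** The best defence is that the comparison is implied: the first sentence of the plan speaks of comparing, and the protocol calls the 60 patients a control. The intention is indeed visible. But that sentence limits itself to patient and surgical characteristics, and an implied comparison fixes no outcome, contrast or adjustment set. Study group might also be among the unlisted confounders; step 2 shows that this would not supply the effect.

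It is also fair to say that this is a small non-randomized survey with no confirmatory claim, and that anxiety is not in the objective. Both are true. Neither removes the gap for satisfaction and understanding, which are.

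Several stronger readings are tempting and should not be adopted:

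- A reader might infer that anxiety is wholly unanalysed. The EQ-5D has an Anxiety/Depression dimension and is a health measure in the planned regression. Only the survey's own anxiety item, a different measure, is left out.
- A reader might count the planned associations and treat the total as the size of the problem. The documents do not fix the number of health measures, satisfaction measures or change scores; different readings give 12 to 54.
- A reader might infer that controls drop out of the health-change model, because their paragraph lists quality-of-life surveys only after surgery. That depends on whether change is taken from before surgery or between later visits, which the plan does not say.
- A reader might take the 23-26% false-positive figure, or the detectable differences, as faults of the present plan. They describe analyses that it does not contain.

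**Conclusion.** The point stands and should be settled before any data are analysed. The plan omits the analysis that its objective and control group exist to provide, and its only model targets a different quantity. This conclusion rests on the text alone and needs none of the assumed figures.

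It does not follow that the study cannot address its objective. The surveys described would support both contrasts, subject to what the two forms contain; neither was available for this review. Nor would the group contrast be a clean causal effect. Control status requires "Patients who do not have a previous CT scan and thus are unable to undergo Surgical Theater Consultation", while 360VR patients "sign consent if they agree to use surgical theater platform", so those with a CT who decline are in neither group. The 360VR group also has extra contact ("Surgical theater appointment and review will take 24 minutes") and answers its survey twice.

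The precision figures are conditional on the assumptions in step 3, and SD units presume a roughly continuous score. On those terms the study could show moderate differences, not small ones.

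**What to change.** Add to the Data Analysis Plan:

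- **(a) Group contrast.** Regress post-consult understanding, satisfaction and survey anxiety on study group, using items common to both forms and a model suited to each item's scale, with 95% intervals. Adjust for the characteristics actually recorded for the first planned analysis. Study Procedures rules out medical records as a data source, and the data list names no such characteristics; if none are recorded, report (a) as unadjusted.
- **(b) Paired change.** Within the 360VR group, estimate the before/after change in understanding, anxiety and, if it is asked both times, satisfaction, with 95% intervals. Report it as an uncontrolled change.
- **Hierarchy.** Name one outcome and one contrast as primary before analysis, for the reason in step 4. Label the health-change regressions secondary.
- **Satisfaction.** State which measure is meant. If the HCAHPS rating is compared by group using the 9-or-10 definition, analyse it as binary.
- **Expectations.** State that no expectations measure is listed, so no conclusion on aligning expectations can be drawn unless the forms contain one.
- **Limitations of (a).** Record the absence of randomization, the dependence of exposure on CT availability and on accepting 360VR, the 24 extra minutes of contact and the repeated survey.

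If the forms share no items, use (b) alone and limit the conclusions to it.

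The cost is analysis wording, with no new visits or patients, provided that the forms share items. Covariate adjustment would need new data collection if no characteristics are now recorded.

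### Outcomes are analysed as change scores, but the 60 controls have no pre-operative QOL survey and the baseline score is not named as a covariate

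*Combined protocol and SAP*

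**What the plan says.** The Data Analysis Plan has one analysis of outcomes. It relates satisfaction and understanding to health status, saying that "changes in each patient-reported health measure will be estimated using linear regression analysis". The same sentence then adds a second kind of model, described only by the words "as well as multivariable linear regression models, adjusting for potential confounders". The other analysis in that section only compares patient and surgical characteristics. No confounder is listed, the baseline score is neither included nor excluded, and the text does not say which variable is dependent.

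Study Procedures sets the QOL schedule separately for each group. In the 360VR group the surveys "will also be given before 360-VR, 6 week post-op, 3 month post op, and 6 month post op". For controls the text is: "QOL surveys (EQ-5D-5L, NDI, Oswestry, RAPT, VR-12) will also be given 6 week post-op, 3 month post op, and 6 month post op". No pre-operative administration is listed for them. Before surgery, controls complete only the Control Group Survey on understanding, anxiety and satisfaction.

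Number of Research Participants gives the total as "We will enroll 90 subjects at UHCMC". It then splits this by group, stating that "30 subjects will receive surgical theater consultation" and that the other 60 are controls. Study Design describes the study as non-randomised.

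**The concern.** Change from pre-operative status needs a pre-operative score. If the control schedule is followed as written, two thirds of the sample cannot enter the plan's only outcome analysis. Nor can baseline health status be compared or adjusted for between the groups. A baseline missed before surgery cannot be recovered later.

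The second issue concerns the patients who do have a baseline. Change is follow-up minus baseline, so it contains baseline with a negative sign. Patients who start with an extreme score tend to move back toward the average. Satisfaction and understanding are not randomised and may differ with initial severity. A model without a baseline term can then credit satisfaction with improvement that reflects only where patients started. Because the confounders are unnamed, whether baseline is adjusted for could be decided after the results are seen.

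**Working it through.** The documents give no significance level, power, SD, correlation or sample-size rationale, so there is no stated figure to reproduce.

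**Step 1. Who can contribute a change score (Study Procedures; Number of Research Participants).**

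| Group | Planned n | QOL before surgery | QOL at 6 weeks, 3 and 6 months | Change from before surgery |
|---|---|---|---|---|
| 360VR | 30 | yes | yes | computable |
| Control | 60 | not listed | yes | not computable |

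Usable: at most 30 of 90 (33%). Lost: 60 of 90 (67%). The usable number falls further with missed visits or skipped items.

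**Step 2. Size of the possible false association.** Assumed, and not in the documents:
- ρ, the baseline-to-follow-up correlation
- g, the correlation of satisfaction with baseline
- equal variances at baseline and follow-up
- a two-sided 5% test
- no link between satisfaction and follow-up once baseline is known

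In standardised units, cov(satisfaction, follow-up) = ρg. The slope of change on satisfaction is therefore ρg - g = -(1 - ρ)g. With ρ = 0.5 and g = 0.3 it is -(0.5)(0.3) = -0.15. Adjusted for baseline, the slope is (ρg - ρg)/(1 - g²) = 0.

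Simulated rejection rates of the unadjusted model at n = 30 (4,000 runs per cell):

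| g | ρ = 0.3 | ρ = 0.5 | ρ = 0.7 |
|---|---|---|---|
| 0 | 4.3% | 4.8% | 5.3% |
| 0.2 | 9.0% | 8.3% | 6.9% |
| 0.3 | 15.3% | 11.7% | 9.4% |
| 0.4 | 24.0% | 18.3% | 13.2% |

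A separate run of 20,000 studies gave 12.4% for the ρ = 0.5, g = 0.3 cell, hence about 12%. Under the same assumptions the baseline-adjusted model rejected in 4.3% to 5.8% across these cells.

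**Step 3. The opposite structure.** Suppose instead that satisfaction correlates 0.3 with both baseline and follow-up, again with ρ = 0.5. The change-score slope is 0.3 - 0.3 = 0. The adjusted slope is (0.3 - 0.5 × 0.3)/(1 - 0.3²) = 0.15/0.91 = 0.165. Simulated rejection at n = 30 was 4.7% for the change score and 15.8% after adjustment. Here baseline adjustment creates an association with change where there is none.

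**Step 4. Precision.** With g = 0, the residual variance is 1 - ρ² with adjustment and 2(1 - ρ) without it. The ratio is (1 + ρ)/2, which is 0.65, 0.75 and 0.85 for ρ = 0.3, 0.5 and 0.7. With g not zero, the large-sample ratio of slope variances is (1 + ρ)/[(1 - g²)(2 - (1 - ρ)g²)]:
- ρ = 0.5, g = 0.3: 1.5/(0.91 × 1.955) = 0.84
- ρ = 0.7, g = 0.4: 1.7/(0.84 × 1.952) = 1.04

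In the second case the simulated standard error at n = 30 was 0.150 adjusted and 0.145 unadjusted, a slight loss.

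**The case against.** **The multivariable model may already contain baseline.** It adjusts for potential confounders, and baseline severity is an obvious one. A reader might infer that the plan leaves baseline out; the text does not support that. What stands is that baseline is not pre-specified, and that the simple model as described has no adjustment.

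**Controls may be covered elsewhere.** The Study Timeline shows a QOL survey at Visit 1 and is not split by group. But it also shows the 360VR consult at that visit, and the listed time points are defined around that consult. The control-group text is the specific one, and it lists post-operative surveys only. If a baseline in controls was intended, the text should say so.

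**The regression may be meant for the 360VR group only, or for change between post-operative visits.** Either is possible, since the plan names neither the analysis set nor the reference time point. On the first reading, controls contribute nothing to the only outcome analysis. On the second, the analysis does not measure change from pre-operative status.

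**The direction of the regression is not stated.** True, but the simple-regression test is the same whichever variable is the outcome, so the rejection rates in Step 2 hold either way. The precision ratios do assume that the health measure is the outcome.

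**Adjustment is not always right.** This stands. Step 3 shows that the ranking of the two models depends on how satisfaction arises, which the documents cannot settle.

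**Conclusion.** The missing control baseline follows directly from the text and needs no assumption beyond reading change as change from before surgery: at most 30 of 90 patients can enter the analysis, or be adjusted for baseline.

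The covariate point is a gap in pre-specification with a conditional consequence. If satisfaction or understanding is related to baseline severity, the unadjusted change-score model can show a false association: slope -0.15 and about 12% false rejection at n = 30 for ρ = 0.5, g = 0.3 and no link to follow-up given baseline. Over ρ from 0.3 to 0.7 and g from 0.2 to 0.4 the rate runs from about 7% to 24%. If g = 0 there is no such bias.

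Three stronger readings are not supported:
- Under the same assumptions the rate is about 30% at n = 90, but the plan as written cannot run that analysis, because controls have no baseline.
- Baseline adjustment does not guarantee a 5% error rate. It does so under the Step 2 structure and fails under that of Step 3.
- A precision gain is not assured. The (1 + ρ)/2 ratio needs satisfaction to be uncorrelated with baseline, and some precision can be lost when the two are strongly related.

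**What to change.** 1. In Study Procedures, give controls the same QOL battery at Visit 1, before surgery, and show this in the Study Timeline and the list of time points. Cost: five surveys at 2 minutes each, about 10 minutes on paper at a visit that controls already attend, or 60 × 10 = 600 minutes over all controls.
2. In the Data Analysis Plan, define change as change from that survey, name the follow-up visit analysed, and state which patients enter the model.
3. For the multivariable model, take the follow-up score as outcome and name that measure's baseline score as a covariate, with the other confounders listed. The coefficient for satisfaction is the same if change is the outcome with baseline in the model, so results can still be presented as change. Cost: one covariate.
4. Report the unadjusted change-score result alongside as a sensitivity analysis. If the two disagree, say so and interpret the association cautiously, since neither model is guaranteed unbiased here. Cost: nearly nothing.

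Item 1 has to be in place before further controls are operated on; items 2 to 4 are text changes to make before the data are analysed.
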